Fairview Investigational Drug Services (IDS), part of M Health Fairview will oversee the preparation of treatment drug and placebo. Identical suspensions (#20) will be prepared in identical syringes and labeled with a deidentified study number coded by site and patient number. A site-specific randomization schema will be created (each site will undergo block randomization in variable permuted blocks by site and age strata). Given significant differences in outcome by age, patients will be randomized by age strata ( $\geq 60$ ,  $< 60$ ). Randomization allocation will be 1:1. IDS will not be blinded to patient randomization. All other members of the study, the participants, and the clinical care team will be blinded to treatment allocation.

4.7 *Provision of study drug to patients:* The local Fairview or HCMC pharmacy will dispense the patient specific supply to each patient after consent has been obtained and

a prescription has been received from an authorized prescriber. The investigational drug or placebo will be provided to the bedside nurse twice daily for the duration of study participation.

4.8 *Study unblinding:* MHealth Fairview, East bank Inpatient Pharmacy UMMC campus, will hold the blind for all subjects on study. In the event of an emergency and unblinding is necessary, study staff can contact [contact], option 1, then option 2. This information is included on each label.

4.9 *Biosafety:* N/A. The intervention is not a biohazard.

4.10 *Stem Cells:* N/A

4.11 *Fetal Tissue:* N/A

4.12 *Use of radiation:* N/A

4.13 *Use of Center for Magnetic Resonance Research:* N/A

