## 10.0 Local Number of participants

*10.1 Locations:* Enrollment will occur on the ED (or designated COVID19 areas) of participating study sites see section 22.1).

*10.2 Number of participants:* We expect to enroll a minimum of 200 participants, with up to 220 participants when considering screen failures and withdrawals.

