## 15.0 Statistical Considerations

- 15.1 *Data Analysis Plan:* All analysis will focus on comparisons between the treatment and control groups. Demographics and other baseline clinical characteristics will be summarized using descriptive statistics. Descriptive statistics will be presented by treatment group using mean, standard deviation, median, and interquartile range (IQR) for continuous variables and frequencies and percentages for categorical

variables. The primary outcome, change in estimated P/F ratio at 7 days, will be summarized by group using the sample mean with 95% asymptotic confidence intervals. Patients discharged home will be given a pulse oximeter and called for the value at 7 days, adjusted for home O2 use as applicable. Patients who died will be penalized with a P/F of 0 (lower values indicate higher degree of respiratory failure) in order to address competing risks. Like respiratory SOFA, an adjustment is applied based on the use of PEEP. For the primary statistical analysis, Treatment groups will be compared using the two-sample t-test for unequal variances and the treatment effect will be summarized by the mean difference between groups. As a secondary statistical approach, we will also jointly model the longitudinal and time to event outcome under the assumption of informative missingness, jointly modeling P/F ratio measured daily and time to death using a shared random effects model. Finally, we will analyze these data on an ordinal scale (the respiratory SOFA score), which is a 0-4 ordinal scale derived from the estimated P/F ratio. In addition, patients who die prior to the day 7 assessment will be assigned a 5 for this analysis.

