Secondary endpoints will be summarized by the sample mean or sample proportion, as appropriate, and compared using the unequal variance two-sample t-test or Chi-square test, as appropriate. Appropriate data transformations will be used to assure that assumptions of all statistical tests are met. Time-to-event endpoints will be summarized by Kaplan-Meier curves and compared using Cox proportional hazards regression. For all endpoints, we will complete secondary analyses comparing for important baseline variables that are unequally distributed between treatment groups. Preplanned subgroup analyses are planned by age (dichotomized at 50 and by decade), history of hypertension, sex, and smoking history, timing of randomization from symptom onset, and respiratory support needed at the time of randomization.

15.2 *Power Analysis:* Assuming a fixed sample size, we analyzed power using a number of assumptions. In general, studies with a similar degree of acute lung injury that we expect in this study have a standard deviation of estimated P/F ratio of 100-125. ARDS trials tend to have smaller SD due to narrowed inclusion criteria, while a single study of H1N1 with a lower severity of illness had a SD of 150. We calculated power for a variety of assumptions. If the SD is 125 or less, we will have >0.8 power to detect a difference in P/F of 50. Differences of less than this are of uncertain clinical significance. This method and outcome has more power than our alternative approach of respiratory SOFA, which is a more crude measure of the estimated P/F ratio.

15.3 **Data Integrity:** The principal investigator will manage oversight of quality control for collected data. Recruitment of subjects will be performed using inclusion/exclusion criteria defined above. Study data will be recorded within a RedCAP database, which is HIPAA compliant, password protected with variable assignable security access and an audit trail consistent with all regulatory requirements for maintenance of clinical trial data. Data summaries and quality control checks will be run routinely.

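### Secondary adjusted analyses of all endpoints pick covariates by observed imbalance between arms; a prognostic set fixed in advance would do better at no cost

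*Combined protocol and SAP*

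**What the plan says.** Section 15.1 makes the primary comparison unadjusted: "Treatment groups will be compared using the two-sample t-test for unequal variances". Secondary endpoints get unadjusted t-tests or chi-square tests, and time-to-event endpoints a Cox comparison. Then, for all endpoints, "we will complete secondary analyses comparing for important baseline variables that are unequally distributed between treatment groups".

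That sentence is the only rule for covariate adjustment in the document. It sets two conditions, importance and imbalance, and defines neither. It gives no list of variables, no threshold and no model.

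Section 4.6 stratifies the permuted blocks by site and by age (60 and over, under 60), on the ground that outcome differs by age. No planned comparison is said to adjust for either factor.

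**The concern.** In a randomised trial, the size of a baseline difference between arms says nothing about whether the variable predicts outcome. If imbalance is required for adjustment, a strong predictor that happens to be balanced is left out, and the precision it would have added is lost. Stratification sharpens this: the age stratum is kept close to balance by design, so the rule would rarely select a factor that the protocol itself regards as prognostic. Respiratory support at randomisation, which section 15.1 lists for subgroups, would enter only if chance unbalanced it.

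The model is also fixed only after baseline data by arm are known. Two analysts following the sentence could reach different adjusted results. At stake are the precision and reproducibility of the supporting adjusted results, not the primary result.

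**Working it through.** **Inputs.** Section 10.2: "We expect to enroll a minimum of 200 participants". Section 4.6: "Randomization allocation will be 1:1". Hence n = 100 per arm. Section 15.2: "If the SD is 125 or less, we will have >0.8 power to detect a difference in P/F of 50", so the effect is 50/125 = 0.4 SD. Two-sided 5% is inferred from "summarized by group using the sample mean with 95% asymptotic confidence intervals". Correlations between covariates and outcome are assumptions, so ranges are shown.

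**1. The plan's own figure.** z = 50 / (125 × √(2/100)) = 50/17.68 = 2.828. Power = Φ(2.828 − 1.960) = Φ(0.868) = 0.807, which agrees with the statement in section 15.2. That section also notes that "a single study of H1N1 with a lower severity of illness had a SD of 150". With SD 150, z = 50/21.21 = 2.357 and power = Φ(0.397) = 0.654.

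**2. Fixed adjustment.** The SD becomes SD × √(1 − R²).
- R² 0.42: 125 × √0.58 = 95.2; z = 50/(95.2 × 0.1414) = 3.71; power 0.960.
- R² 0.12: 125 × √0.88 = 117.3; z = 3.015; power 0.854 by this normal approximation (about 0.845 in simulation).

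**3. The rule with one covariate.** Let X be the z-score of the imbalance, c the trigger and ρ the correlation with outcome. Given X = x, the unadjusted statistic is normal with mean z + ρx and variance 1 − ρ². The procedure's rejection rate is P(|X| > c) × (adjusted power), plus the integral over |x| < c of φ(x) × (conditional unadjusted rejection rate). A standardised mean difference (SMD) of 0.2 corresponds to c = 0.2 × √50 = 1.41, and 0.1 to c = 0.71. For ρ = 0.5 and SD 125:

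| Trigger | Type I error | Power | Share of available gain |
|---|---|---|---|
| p<0.05 | 0.043 | 0.819 | 12% |
| p<0.10 | 0.040 | 0.827 | 20% |
| SMD>0.2 | 0.038 | 0.836 | 29% |
| SMD>0.1 | 0.038 | 0.869 | 63% |
| Always adjust | 0.05 | 0.904 | 100% |

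The share is, for example, (0.8187 − 0.8074)/(0.9042 − 0.8074) = 0.117. Over ρ from 0.3 to 0.7 the rule's type I error is 0.027 to 0.048. It falls below 5% because, when X is small, the unadjusted statistic varies less than its nominal standard error assumes. When adjustment is triggered, the adjusted test itself is correctly sized.

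**4. Eight candidates, total R² 0.42** (0.25, 0.09, 0.04, 0.04 and four of zero). The fixed set is the four prognostic covariates. Each setting used 5,000 simulated trials; ranges span two sets of runs. Simulation error is about 2√(0.03 × 0.97/5000) = 0.005 for type I error and 2√(0.85 × 0.15/5000) = 0.010 for power.

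| Analysis | Type I error | Power |
|---|---|---|
| Unadjusted | about 0.05 | 0.80–0.81 |
| Rule, p<0.05 | 0.038 | 0.82–0.83 |
| Rule, p<0.20 | 0.026–0.029 | 0.84–0.86 |
| Rule, SMD>0.2 | 0.029 | 0.85 |
| Rule, SMD>0.1 | 0.025 | 0.90 |
| Fixed set | about 0.05 | 0.95–0.96 |

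At the p<0.05 trigger, nothing is selected in 0.95⁸ = 66% of trials, and the strongest predictor is selected in only about 5%.

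**5. Weaker covariates, total R² 0.12.** The rule gives type I error 0.044 to about 0.05 and power 0.80 to 0.82; the fixed set gives power of about 0.845.

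**The case against.** The written rule asks for *important* variables, so a sensible analyst would not adjust for noise, and half the candidates in step 4 have no prognostic value. This is fair, but it does not rescue the rule, because imbalance is still required. With every candidate prognostic and total R² 0.42, the rule gives type I error 0.029 to 0.040 and power 0.81 to 0.91, against about 0.05 and 0.95 to 0.96 for a fixed set.

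Three stronger readings are tempting, and the documents do not support them.

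- *The rule produces false positives.* As a procedure it errs on the conservative side, and at R² 0.12 it is nearly correct. Type I error reaches 0.049 to 0.064 only if the more favourable of the unadjusted and adjusted p-values is reported. The protocol does not plan that, although its undefined rule does not rule it out.
- *The rule forfeits almost all the power available from adjustment.* With one covariate this holds at a strict p<0.05 trigger, where 8 to 12% of the gain is recovered (SD 150 and 125). At SMD>0.1 it recovers about 55 to 68%. The protocol states no trigger.
- *The main conclusion is compromised.* The primary test is the unadjusted t-test, and secondary endpoints have their own unadjusted or Cox comparisons. Only analyses labelled secondary are touched.

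Two further limits stand. Only normally distributed continuous outcomes were calculated. Nothing here measures the effect on mortality or other binary and time-to-event endpoints, or on P/F with deaths scored as zero. A fixed set can also overfit a sparse endpoint: section 18.3 assumes 10% mortality, or 0.10 × 200 = 20 deaths.

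**Conclusion.** The point holds for the secondary adjusted analyses and is worth acting on because the change is free. Selection by imbalance omits balanced predictors, almost always including the age stratum, and leaves the model open until data by arm are seen. For a continuous outcome with 100 per arm and an effect of 0.4 SD, power falls short of a fixed set by 0.06 to 0.14 at R² 0.42 (0.96 − 0.90 to 0.96 − 0.82), and by about 0.025 to 0.045 at R² 0.12 (0.845 − 0.82 to 0.845 − 0.80). The type I error is conservative at the higher R² and close to nominal at the lower. These sizes rest on assumed R² values, normal outcomes and a two-sided 5% test. The direction does not depend on the threshold; the size does. The stated power of the primary analysis reproduces and is unaffected.

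**What to change.** Replace the sentence in section 15.1 with:

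> Adjusted secondary analyses of each endpoint use a fixed covariate set chosen before unblinding, whatever the observed balance: the randomisation factors (age stratum, and site with small sites pooled), the entry value of the endpoint where one exists, and respiratory support at randomisation collapsed to a few levels. Linear models are used for continuous, logistic for binary and Cox for time-to-event endpoints. For mortality a reduced set (age stratum and collapsed respiratory support) is used because few deaths are expected. Baseline imbalance is described but not used to select covariates.

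The pooling of sites and the levels of respiratory support should be written down at the same time. The variables are already collected (section 1.6, the randomisation strata in section 4.6 and the table of events in section 5.6). The cost is a short paragraph and one decision before unblinding. It needs no extra patients or data and leaves the primary analysis unchanged.

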## 8.0 Study Population

### 8.1 *Inclusion Criteria*

- Presumptive positive laboratory test for Covid-19 based on local laboratory standard
- Age greater than or equal to 18 years of age
- Admission to the hospital with a respiratory SOFA  $\geq 1$  and increased oxygen requirement compared to baseline among those on home O2
- Randomization within 48 hours of presentation of hospital admission or within 48 hours of a positive test result, whichever is later

8.2 *Rationale for inclusion criteria:* This is a pragmatic trial looking to enroll a diverse cohort of participants so the results may be broadly applicable to a wide patient population if efficacious. We do not have sufficient data to support lack of efficacy in a specific subgroup at this time to justify their exclusion. However, a respiratory SOFA of at least 1 is included to provide room for improvement to meet the primary efficacy endpoint. Patients on home oxygen therapy must demonstrate an acute deterioration under the same rationale. While we currently propose to exclude children due to insufficient time at the writing of this protocol to closely scrutinize safety and dosing in that group, along with logistical challenges of having different doses, we have plans to evaluate the possibility of expanding to include that patient population as soon as logistically feasible.

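### Does section 15.2 need a power figure, or a variance check during enrolment, for an SD above 125 when it also cites an SD of 150?

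*Combined protocol and SAP*

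**What the plan says.** Section 15.2 begins "Assuming a fixed sample size, we analyzed power using a number of assumptions". It reports that studies with comparable lung injury "have a standard deviation of estimated P/F ratio of 100-125". It then remarks that "ARDS trials tend to have smaller SD due to narrowed inclusion criteria", and that "a single study of H1N1 with a lower severity of illness had a SD of 150". One result is reported: "If the SD is 125 or less, we will have >0.8 power to detect a difference in P/F of 50". Differences smaller than 50 are treated there as clinically doubtful.

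The parts that bear on this are:

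- **Size.** Sections 10.2 and 23.1 plan at least 200 participants. The ceiling of 220 allows for screen failures and (in 10.2) withdrawals. Section 4.6 sets 1:1 allocation.
- **Population.** Section 8.2 says "This is a pragmatic trial looking to enroll a diverse cohort of participants so the results may be broadly applicable", and that "a respiratory SOFA of at least 1 is included to provide room for improvement". Section 15.1 describes that score as one "which is a 0-4 ordinal scale derived from the estimated P/F ratio".
- **Outcome.** Section 15.1 analyses the change in estimated P/F at day 7 with an unequal-variance t-test. Deaths are scored as P/F 0, and discharged patients contribute a home oximeter value.
- **Monitoring.** Section 18.3 schedules safety looks at 10%, 20% and 30% of enrolment, and a look at 50% for safety, efficacy and futility. It mentions no review of the SD. The DSMB charter it refers to is not among the documents.

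**The concern.** The paragraph quotes SDs up to 150 but stops its power statement at 125, the top of the range it expects. A reader cannot learn from it what happens at the highest value cited. Two features of the plan could push the SD up. Entry is broad, whereas the paragraph itself links narrow entry with small SDs. The outcome also runs from deaths at 0 to patients already at home.

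If the SD of the analysed outcome were 150, the trial would miss a true 50-point difference about 35% of the time instead of just under 20%. A shortfall of that kind can be repaired only while enrolment is open, and no step in the documents would detect it.

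**Working it through.** **Inputs.** Difference 50 (15.2); 100 per arm, or 110 if all 220 are analysed (10.2, 23.1, 4.6); SDs 100, 125 and 150 (15.2), with 130 and 140 added as intermediate values. Alpha is not stated. Two-sided 0.05 is assumed, in line with the 95% intervals in 15.1.

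**1. The plan's own figure.** Standard error = SD × √(2/n). Power ≈ Φ(50/SE − 1.96).

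At SD 125: SE = 125 × √(2/100) = 17.68; 50/17.68 = 2.83; 2.83 − 1.96 = 0.87; Φ(0.87) = 0.807. The noncentral t with 198 df gives 0.804. The claim of more than 0.8 is reproduced.

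**2. Other SDs** (noncentral t):

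| SD as analysed | Power, 200 analysed | Power, 220 analysed | Total for 0.80 |
|---|---|---|---|
| 100 | 0.94 | 0.96 | 128 |
| 125 | 0.80 | 0.84 | 200 |
| 130 | 0.77 | 0.81 | 216 |
| 140 | 0.71 | 0.75 | 250 |
| 150 | 0.65 | 0.69 | 286 |

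At SD 150 the normal formula gives SE = 21.21; 50/21.21 − 1.96 = 0.40; Φ = 0.654. A one-sided 0.05 test would give 0.762.

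The difference detectable with 80% power at SD 150 is 2.802 × 21.21 = 59.4 (59.7 with the t). The largest SD that keeps 0.80 with 200 analysed is 50/(2.802 × 0.1414) = 126.2 (125.6 with the t). With 220 analysed it is 131.8 (t).

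**3. Is 150 the SD to plan for?** The documents leave two things open.

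- *Change or level.* The cited SDs are for the P/F ratio, but 15.1 analyses change. If they are SDs of the level, SD of change = SD × √(2(1 − r)), where r is the correlation between baseline and day 7. At level SD 150, r = 0.5 gives 150 and power 0.65; r = 0.7 gives 150 × √0.6 = 116.2 and power 0.86. The values of r needed for 0.80 are 0.21, 0.50 and 0.65 at level SD 100, 125 and 150.
- *Deaths at 0.* On the level scale, with death share m and survivor mean μ, SD² = (1 − m) × s² + m(1 − m) × μ², where s is the survivor SD. Take m = 5% or 10% (18.3 assumes 10% baseline mortality) and assume μ between 200 and 300. With s = 125, the overall SD is 129–138 at 5% and 133–149 at 10%. With s = 100, it is 107–117 and 112–131. The documents do not say whether the cited SDs already include such zeros.

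So the SD may fall on either side of 125.

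**4. What a variance check would gain.** A blinded check was simulated: the pooled variance of the first 100 outcomes sets the final size between 100 and 143 per arm (normal outcome, no early stopping, 40,000 runs). Compared with a fixed 200, power goes from 0.806 to 0.823 at SD 125, from 0.710 to 0.788 at SD 140, and from 0.652 to 0.775 at SD 150. Type I error stays at about 0.05. The mean total is 211 at SD 125, 247 at SD 140 and 270 at SD 150.

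**The case for a change.** The strongest case for a change is this. Two hundred analysed patients leave no reserve above the expected range, and 10.2 already assigns the extra 20 to losses. Scoring deaths as 0 and admitting patients broadly both tend to widen the spread. A blinded look at the variance is a recognised safeguard, leaves the t-test untouched, and could fall where a look is already planned.

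The thin margin stands, and so does the figure of 0.65 at SD 150. The rest is weaker:

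- Section 15.2 chooses its range by severity of illness and separates the 150 on that ground. The remark about narrow entry concerns ARDS trials, and may only explain why their SDs are lower.
- The illustration with deaths rests on an assumed survivor mean and SD. The same formula also gives totals well below 125.
- The check is not just one added paragraph. It would have to be kept apart from the by-arm safety looks at 10%, 20% and 30%. The 50% efficacy and futility look would need new timing, since 100 of 286 is 35%. Rules would be needed for missing day-7 values. Keeping the present 10% allowance for losses would take 286 to about 315 (286 × 1.1). Even then, power at SD 150 reaches only 0.775.

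Whether fuller power results exist elsewhere cannot be settled. Section 15.2 says several scenarios were calculated. Figures were not available for this check, and one without a caption stands just before section 15.

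**Conclusion.** The plan claims more than 0.8 power on an explicit condition, and under that condition the design delivers it (0.804 with 200 analysed, two-sided 0.05 assumed). If the SD of the outcome as analysed were 150, power would be about 0.65 and the detectable difference about 60. However, the documents present 150 as a value from one less severe study, and nothing in them shows that 125 will be exceeded.

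Holding the sample size fixed is a stated and fair trade-off. Re-estimation would spend up to 86 more analysed patients (286 − 200) to protect a power level that the plan never promised at that SD, and it would disturb the interim schedule. It remains open to the sponsor as a design choice. Quoting the power at SD 150 would be a courtesy to readers: it changes neither the analysis nor the size, and anyone can derive it from the figures given.

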## 16.0 Health Information and Privacy Compliance

### 16.1 Select which of the following is applicable to your research:

- My research does not require access to individual health information and therefore assert HIPAA does not apply.
- I am requesting that all research participants sign a HIPCO approved HIPAA Disclosure Authorization to participate in the research (either the standalone form or the combined consent and HIPAA Authorization).
- I am requesting the IRB to approve a Waiver or an alteration of research participant authorization to participate in the research.
- An external IRB (e.g. Advarra) is reviewing and we are requesting use of the authorization language embedded in the template consent form in lieu of the U of M stand-alone HIPAA Authorization. Note: External IRB must be serving as the privacy board for this option.

### 16.2 Identify the source of Private Health Information you will be using for your research (Check all that apply)

- I will use the Informatics Consulting Services (ICS) available through CTSI (also referred to as the University's Information Exchange (IE) or data shelter) to pull records for me

MEDICAL PROTOCOL (HRP-590)

SHORT PROTOCOL TITLE: Randomized control trial of losartan for inpatients with COVID-19

VERSION DATE:22APR2020

- I will collect information directly from research participants.
- I will use University services to access and retrieve records from the Bone Marrow Transplant (BMPT) database, also known as the HSCT (Hematopoietic Stem Cell Transplant) database.
- I will pull records directly from EPIC.
- I will retrieve record directly from axiUm / MiPACS
- I will receive data from the Center for Medicare/Medicaid Services
- I will receive a limited data set from another institution
- Other. Describe: CTSI's BPIC will be used to pull structured data directly from EPIC into redcap (ED vitals, labs, etc.), or data will be transcribed by coordinators into our Redcap research database. Study coordinators will contact patients daily to obtain data and will input it directly into the Redcap research database.

16.3 *Explain how you will ensure that only records of patients who have agreed to have their information used for research will be reviewed:* Study coordinators and BPIC will review if patients have opted out of research by using the opt-out flag within Epic to determine research status. Only patients that have opted-in to research or have expressed that they wish to delay opt-out status will be included in this study.

16.4 *Approximate number of records required for review:* 220.

16.5 *Please describe how you will communicate with research participants during the course of this research. Check all applicable boxes:*

- This research involves record review only. There will be no communication with research participants.
- Communication with research participants will take place in the course of treatment, through MyChart, or other similar forms of communication used with patients receiving treatment.
- Communication with research participants will take place outside of treatment settings. If this box is selected, please describe the type of communication and how it will be received by participants.

16.6 *Explain how the research team has legitimate access to patients/potential participants:* Informed consent will be obtained from patients granting access to clinical data for study participants.

16.7 *Location(s) of storage, sharing and analysis of research data, including any links to research data (check all that apply).*

In the data shelter of the [Information Exchange \(IE\)](#)

Store       Analyze       Share

In the Bone Marrow Transplant (BMT) database, also known as the HSCT (Hematopoietic Stem Cell Transplant) Database

Store       Analyze       Share

MEDICAL PROTOCOL (HRP-590)

SHORT PROTOCOL TITLE: Randomized control trial of losartan for inpatients with COVID-19

VERSION DATE:22APR2020

In REDCap (recap.ahc.umn.edu)

Store  Analyze  Share

In Qualtrics (qualtrics.umn.edu)

Store  Analyze  Share

In OnCore (oncore.umn.edu)

Store  Analyze  Share

In the University's Box Secure Storage (box.umn.edu)

Store  Analyze  Share

In an AHC-IS supported server. Provide folder path, location of server and IT Support Contact:

Store  Analyze  Share

In an AHC-IS supported desktop or laptop.

Provide UMN device numbers of all devices:

Store  Analyze  Share

Other. Describe:

Indicate if data will be collected, downloaded, accessed, shared or stored using a server, desktop, laptop, external drive or mobile device (including a tablet computer such as an iPad or a smartdevice (iPhone or Android devices) that you have not already identified in the preceding questions

will use a server not previously listed to collect/download research data

will use a desktop or laptop not previously listed

will use an external hard drive or USB drive ("flash" or "thumb" drives) not previously listed

will use a mobile device such as an tablet or smartphone not previously listed

*16.8 Consultants. Vendors. Third Parties. N/A*

*16.9 Links to identifiable data:* All information that identifies study subjects will be handled in accordance with regulatory bodies including HIPAA regulations and the CIIRB. This information will be made only available to the principal investigators and study personnel who directly participate in the research calls. Prior to enrollment, participants will sign an authorization to use and disclose PHI for research purposes. All staff will have been trained in the use of PHI. Subjects will be assigned a random subject ID number and a link between identifiers will be maintained in an excel log which will be stored in a secure folder in the AHC-IE data shelter, the University of Minnesota's most secure healthcare research environment. Only the principal investigators and study nurses will have access to this file.

16.10 *Sharing of Data with Research Team Members:* A fully de-identified (of all PHI) database will be generated which will be used for statistical analysis and for monitoring by our DSMB. This database will exist within Redcap.

16.11 *Storage and Disposal of Paper Documents:* At this time we do not anticipate any paper documents related to this study. Everything, including consents will be done electronically. If the need for paper collection templates becomes evident, these documents will be stored in locked rooms where only study personnel have access. They will be maintained for 7 years as legally required, after which time they will either be destroyed or moved to long-term storage.

